SOP(s)	Standard Operating Procedure(s)

PROTOCOL BODY

1. Study Objective

The objective of this study is to evaluate the efficacy (changes in dentinal hypersensitivity) and safety (oral soft tissue evaluation) after use of one of four dentifrices in subjects with pre-existing hypersensitivity over an 11-week period.

2. Overall Study Design and Plan

This is a randomized, controlled, single center, double-blind study to assess efficacy (the changes in dentinal hypersensitivity) and safety (oral soft tissue evaluation) of four dentifrices with different desensitizing technologies over 8 weeks of assigned product use, followed by three weeks of washout product use (Colgate Cavity Protection). After informed consent, approximately 150 subjects with a history of tooth sensitivity will be evaluated to enroll a target population of approximately 120 healthy adult volunteers with current dentinal hypersensitivity. Subjects will be randomized to either an experimental potassium oxalate dentifrice, marketed potassium nitrate dentifrice, marketed stannous fluoride dentifrice, or a regular anticavity dentifrice (negative control). Subjects will use assigned product for 8 weeks. After 8 weeks, all subjects will use Colgate Cavity Protection and come back 3 weeks later (Week 11) to have their dentinal hypersensitivity re-evaluated. Dentinal hypersensitivity will be measured by a standard thermal challenge (cold air response measure via Schiff Index) and probing force (calibrated Yeaple probe). Measurements will be taken at Baseline (before any treatment), Day 3, Week 2, Week 4, Week 8 and Week 11. Safety will be assessed from clinical examination of the oral soft tissue. A digital image of the oral soft tissue and hard tissue may be taken, at the discretion of the examiner.

Procedure	VISIT 1 Screening/Baseline	VISIT 2 Day 3	VISIT 3 WEEK 2 (±2 DAYS)	VISIT 4 WEEK 4 (±2 DAYS)	VISIT 5 WEEK 8 (± 2 DAYS)	VISIT 6 WEEK 11 (± 2 DAYS)
Informed Consent	Х					
Medical History Review	Х					
Confidentiality Disclosure Agreement (CDA)	Х					
Demographics	Х					
Questionnaire*	Х				Х	
Documentary Image (optional)	х	х	х	х	х	Х
Inclusion/Exclusion Criteria	х					
Continuance Criteria		Х	Х	Х	Х	Х
Oral Examination	Х	Х	Х	Х	Х	Х
Tactile Challenge	Х	Х	Х	Х	Х	Х
Cold Air Challenge	Х	Х	Х	Х	Х	Х
Product Distribution	Х				Х	
Wash-out Product Distribution					Х	
Product Usage Instructions	X				Х	

Post Treatment Oral Exam	х					
Product Return					Х	Х
General Comments	Х	Х	Х	Х	Х	Х
AEs	Х	Х	Х	Х	Х	Х

Subjects will return to the site after 3 days. Continuance criteria will be assessed. A comprehensive oral examination will then be conducted to evaluate the oral and perioral region, including hard and soft tissues. Tactile sensitivity will be assessed using a standard calibrated Yeaple probe beginning at 10 g probing force. Approximately 5 minutes later, thermal sensitivity will be assessed using a standard cold air challenge (Schiff Index). All general comments and AEs, if any, will be recorded on the appropriate eCRF.

Week 2 (+/- 2 days), Visit 3

Subjects will return to the site after 2 weeks. Continuance criteria will be assessed. A comprehensive oral examination will then be conducted to evaluate the oral and perioral region, including hard and soft tissues. Tactile sensitivity will be assessed using a standard calibrated

Yeaple probe beginning at 10 g probing force. Approximately 5 minutes later, thermal sensitivity will be assessed using a standard cold air challenge (Schiff Index). All general comments and AEs, if any, will be recorded on the appropriate eCRF.

Week 4 (+/- 2 days), Visit 4

Subjects will return to the site after 4 weeks. Continuance criteria will be assessed. A comprehensive oral examination will then be conducted to evaluate the oral and perioral region, including hard and soft tissues. Tactile sensitivity will be assessed using a standard calibrated Yeaple probe beginning at 10 g probing force. Approximately 5 minutes later, thermal sensitivity will be assessed using a standard cold air challenge (Schiff Index). All general comments and AEs, if any, will be recorded on the appropriate eCRF

Week 8 (+/- 2 days), Visit 5

Subjects will return to the site after 8 weeks and will bring their kit box with them. Continuance criteria will be assessed, and subjects will be asked to complete a post-treatment questionnaire. A comprehensive oral examination will then be conducted to evaluate the oral and perioral region, including hard and soft tissues. Tactile sensitivity will be assessed using a standard calibrated Yeaple probe beginning at 10 g probing force. Approximately 5 minutes later, thermal sensitivity will be assessed using a standard cold air challenge (Schiff Index). All general comments and AEs, if any, will be recorded on the appropriate eCRF. Subjects will return treatment products and will be given a new kit box with washout product to use for three weeks.

Week 11 (+/- 2 days), Visit 6

Subjects will return to the site after 11 weeks and will bring their kit box with them. Continuance criteria will be assessed. A comprehensive oral examination will then be conducted to evaluate the oral and perioral region, including hard and soft tissues. Tactile sensitivity will be assessed using a standard calibrated Yeaple probe beginning at 10 g probing force. Approximately 5 minutes later, thermal sensitivity will be assessed using a standard cold air challenge (Schiff Index). All general comments and AEs, if any, will be recorded on the appropriate eCRF. Subjects will receive a bottle of Crest Kids Anti-Cavity fluoride rinse to take home and use at their discretion. Subjects will return wash-out products, and a subject accountability form will be completed.

Subject Accountability

A subject accountability form will be completed for each subject. If, for any reason, a subject does not complete the study, an explanation will be entered on the Subject Accountability eCRF. All data gathered on the subject prior to discontinuation will be made available to the Sponsor.

General Comments and Adverse Event Recording

General comments and AEs may be recorded at any time during the study. All serious AEs will be recorded. In addition, non-serious oral-related AEs will be recorded. Any recorded AE that remains unresolved by study end should be followed up until resolution by the Investigator and the resolution should be documented as source documentation by the Investigator. If a subject is unreachable to determine whether the AE has been resolved, the attempts to contact the subject should be documented as source documentation by the Investigator.

Optional Documentary Image

Business Use

Subjects may have a documentary image of their oral cavity taken to document any research findings, at the discretion of the examiner.

3. Inclusion Criteria

In order to be included in the study, each subject must:

- 1. be at least 18 years of age;
- 2. provide written informed consent prior to participation and be given a signed copy of the informed consent form;
- 3. sign a Confidentiality Disclosure Agreement (CDA);
- 4. be in good general health as determined by the Investigator/designee;
- 5. agree not to participate in any other oral/dental product studies during the course of this study;
- 6. agree to delay any dentistry (including dental prophylaxis) until the study has been completed;
- 7. agree to refrain from the use of any non-study oral hygiene products*;
- 8. exhibit adequate oral hygiene (i.e., brush teeth daily and exhibit no signs of oral neglect);
- 9. have an absence of extensive calculus above the gum line;
- 10. agree to return for all scheduled visits and follow study procedures; and
- 11. have two teeth with a Schiff sensitivity score > 1 in response to air challenge and a Yeaple probe score of 10-20 g in response to tactile challenge. (If these two eligible teeth are located in the same quadrant, they have to be separated by 2 other teeth.)

* Regular floss users will be permitted to continue flossing in their customary manner. However, those subjects who do not report regular floss use will not be permitted to floss for the duration of the study.

4. Exclusion Criteria

Subjects are excluded from study participation where there is evidence of:

- 1. having taken anti-inflammatory, analgesic, or psychotropic drugs, chronically;
- 2. chronic medical debilitating disease associated with constant or intermittent episodes of daily pain;
- 3. any home-care bleaching, whitening products or have had a professional bleaching treatment within 4 weeks of the Baseline visit;
- 4. dental prophylaxis within 2 weeks prior to Baseline visit;
- 5. having received professional desensitizing treatment or having used over-the-counter desensitizing products within 6 weeks of the Baseline visit;
- 6. having periodontal surgery, orthodontic treatment, or teeth restored in the preceding three months;
- 7. having teeth or periodontium with pathology or defects likely to cause pain;
- 8. having a history of allergies or hypersensitivity to ingredients in commercial dental products or cosmetics;
- 9. self-reported pregnancy or lactation;
- having self-reported eating disorders, uncontrolled gastroesophageal reflux disease (GERD or Acid Reflux), excessive dietary or environmental exposure to acids, or other systemic conditions that are predisposing to dentinal hypersensitivity;
- 11. history or presence of kidney disorders, kidney stones, have celiac disease, inflammatory bowel disease (ulcerative colitis or Crohn's disease), chronic pancreatitis, have had intestinal

or weight-loss surgery, or if have stomach or intestinal problems that keep them from absorbing certain foods or nutrients;

- 12. any diseases or condition that might interfere with the safe participation in the study;
- 13. inability to undergo study procedures;
- 14. having severe xerostomia;
- 15. having had active caries within the 12 months;
- 16. having high risk for caries development (rampant caries, multiple dental restorations, crowns with compromised margin) per examiners discretion;
- 17. teeth will be excluded from study measurements if they:
 - have deep, defective, or facial restorations;
 - have full crowns, extensive caries, cracked enamel, or are abutment teeth for fixed or removable prosthesis;
 - present with tendency for spontaneous bleeding;
 - have been scaled/root planed or restored within the past 3 months.

5. Continuance Criteria

Subjects may be excluded from the study or the analysis due to:

- 1. started taking anti-inflammatory, analgesic, or psychotropic drugs, chronically;
- 2. developed chronic medical debilitating disease associated with constant or intermittent episodes of daily pain;
- 3. a dental prophylaxis or other dentistry since the last visit;
- 4. use of any non-study oral hygiene products since the last visit;
- 5. reported pregnancy since the last study visit;
- 6. participation in any other oral care study since the last visit; or
- 7. being unable or unwilling to comply with study procedures since the last study visit.

6. Identity of Investigational Product(s)

- **Control:** Colgate[®] Cavity Protection toothpaste (0.76% sodium monofluorophosphate) and Oral-B[®] Indicator soft toothbrush.
- Experimental Potassium oxalate toothpaste and Oral-B[®] Indicator soft toothbrush.
- Crest[®] Pro-Health Sensitive and Enamel Shield (0.454% stannous fluoride) toothpaste, and Oral-B[®] Indicator soft toothbrush.
- Sensodyne[®] Extra Whitening toothpaste (5% potassium nitrate) and Oral-B[®] Indicator soft toothbrush.

Week 8-11 Washout Product:

 Colgate[®]Cavity Protection Toothpaste (0.76% sodium monofluorophosphate) and Oral-B[®] Indicator soft toothbrush.

7. Method of Assigning Subjects to Treatment Groups

Study	Ν	n/group	B&A	PRA	Strata	Cut-offs
Design			Program	Block		
_			_	Size		
Dorallal	120	30 per		4	Pre-treatment Schiff	
Falallel	120	group	Yes	4	Index	≤2.5 or >2.5

		Pre-treatment Yeaple Probe	=10 or >10
		Age	<40 or ≥40
		Gender	Male or Female

B&A Program

Eligible subjects will be stratified based on the Pre-treatment Schiff Index and Yeaple probe sensitivity scores, age, and gender. Within strata, subjects will be randomly assigned to one of the treatment groups using an encoded program supplied by the Sponsor. This assignment process and the distribution of test products will be conducted in a protected area that will ensure blinding of the examiner to the identity of the test products. Product distribution and product return will be recorded on the Product Distribution Log provided by the Sponsor. Subjects from the same household will be assigned to the same treatment group.

8. Product Usage

Subjects will be instructed to brush twice daily. Subjects will be instructed to apply at least a 1inch strip of the toothpaste onto the toothbrush and to brush thoroughly for 1 minute and expectorate.

All subjects will be instructed to use only the assigned products in place of normal oral hygiene for the duration of the study.

9. Blinding, Labeling, and Shipping Plan

The identity of the toothpaste will be disguised. Kit boxes will contain 2 tubes of toothpaste, 1 toothbrush, 1 timer and subject instructions. Week 8 kit boxes will contain 1 tube of toothpaste, and subject instructions (subjects will use the same timer from previous kit box) for the 3-Week washout period.

The kit boxes will be labeled with a unique kit number. Control and test kit boxes will be identically sized; the kit box labels will be identical except for a unique kit number used for assignment. Kit box labels will also contain the study number, emergency phone number, distributor name/address, appropriate caution statements, content statement and other information as required by internal regulations and clinical SOPs. The shipping containers will be labeled with the clinical site address and a content statement listing study number and kit box numbers contained within. Supplemental products will be provided to site.

The site will be provided with a code breaker report in a sealed envelope. The sealed code breaker report contains documents that list the kit box number or treatment code while the identity of the treatment products is hidden by an opaque scratch-off seal. If the study blind needs to be broken, an individual subject's investigational product may be ascertained by opening the sealed code breaker report, locating the subject's kit box number or treatment code and scratching off the opaque seal to reveal the treatment identity. The sealed code breaker report will be opened if a clinically serious AE occurs or management of the subject requires knowledge of the identity of the investigational product. The Investigator should immediately inform the Sponsor that the code will be broken and record the date, time and reason for breaking the code in writing. After the study is complete and the study database has been finalized and locked, the site will return

the code breaker report to the Sponsor using the self-addressed, stamped envelope provided by the Sponsor.

10. Determination of Sample Size

Power analyses were conducted with α =0.05, using a 2-sided test. Up to 120 subjects will be enrolled in the study assuming ~5% dropout rate. Data were utilized from a similarly designed study with the same examiner and endpoints (2018095). Twenty-eight subjects per group completing this trial should provide at least 90% power to detect a difference in Schiff mean scores of at least 0.80 units between treatments assuming the variability(s) of Schiff score is 0.88. Assuming the variability(s) of Yeaple score is 12.44, a sample size of 28 subjects per group should provide at least 90% power to detect a difference in Yeaple score of at least 10.97 units between treatments.

11. Safety Variables

Safety Observations and/or Measurements

Safety will be assessed by the absence of irreversible side effects.

Oral Examination

Assessment of the oral soft tissue is conducted via a visual examination of the oral cavity and perioral area utilizing a standard dental light, dental mirror, and gauze. The structures examined include the gingiva (free and attached), hard and soft palate, oropharynx/uvula, buccal mucosa, tongue, floor of the mouth, labial mucosa, mucobuccal/mucolabial folds, lips, and perioral area. Assessment of the oral hard tissues will be conducted via a visual examination of the dentition and restorations utilizing a standard dental light, dental mirror, and air syringe. All abnormal findings will be recorded and categorized by their location; hard tissue findings will be categorized as "other." An AE will be recorded if a new abnormal finding is noted after product distribution or any previously noted abnormal finding increases in severity during the treatment period.

12. Efficacy Variables

Yeaple Probe Calibration

The Yeaple probe will be calibrated each day subjects are seen and in accordance with the site's internal SOPs. The settings should be recorded, dated, and initialed by the person performing the calibration on an appropriate form. A new form will not be necessary for each calibration; however, care should be taken so as not to use a different day's force settings. This record will serve as the guide for the force setting for that day's examinations.

Tactile Threshold Determination

Tactile sensitivity at test teeth will be assessed at the Baseline, Week 2 and Week 4 and Week 8 visits using the Yeaple probe test. A #16 explorer tip will be used with the Yeaple probe. The tip will be kept perpendicular to the root surface of the tooth being tested. The tip will be moved horizontally across the facial surface over the sensitive area. Two horizontal sweeps across the entire facial surface are made at each force setting.

At Baseline (before treatment), testing will be performed beginning at 10 g. The examiner will record tactile scores for responding teeth. After treatment, testing will begin at 10 g and

increase by 10 g to a maximum of 50 g. Each successive challenge shall increase until a "yes" response will be repeated. If a second "yes" is not obtained, the force setting is increased to the next step and continued until a force is found which elicits two consecutive "yes" responses, which will be recorded as the threshold on the Tactile Sensitivity Score form. If no sensitivity is found up to 50 g, 50 will be recorded as the threshold.

Cold Air Challenge

A one second application of cold air will be delivered onto each tooth tested from a standard dental unit syringe.

Schiff Index Sensitivity Scale

The examiner will record the Schiff Index score corresponding to the response to the cold air challenge.

	Schiff Index Sensitivity Scale					
SCORE	Criteria					
0	Tooth/Subject does not respond to stimulus					
1	Tooth/Subject responds to stimulus, but does not request discontinuation of stimulus					
2	Tooth/Subject responds to stimulus and requests discontinuation or moves from stimulus					
3	Tooth/Subject responds to stimulus, considers stimulus to be painful, and requests discontinuation of the stimulus					

13. Hypothesis

The following hypotheses will be tested for each post-treatment assessment.

Null: There is no mean score difference between treatment groups.

Alternative:

There is a mean score difference between treatment groups.

For each treatment group, the following hypothesis will be tested for each post-treatment assessment.

Null:The post-treatment mean is equal to the pre-treatment mean.Alternative:The post-treatment mean is not equal to the pre-treatment mean.

The Schiff Index Sensitivity Scale at Week 4 will be of primary interest.

14. Statistical and Analytical Plans

The following statistical analyses will be performed for the sensitivity data (Schiff Index and Yeaple Tactile Sensitivity). Sensitivity scores will be averaged amongst test teeth within each subject for each assessment before and after treatment. For each treatment group and assessment, mean post-treatment assessments will be compared to pre-treatment using a statistical analysis for paired data that is either non-parametric or parametric (e.g., Wilcoxon signed rank test or one sample t-test). For each post-treatment assessment, mean comparisons between treatment groups will be analyzed using analysis of covariance with the

baseline score as a covariate with either non-parametric or parametric methods. If necessary, a mathematical transformation to the data may be performed to aid statistical assumptions associated with parametric analysis methods. Statistical comparisons will utilize two-sided testing with a 5% significance level. Demographic and safety data will also be summarized. Additional statistical methods may be used to further investigate these data.

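### Each ANCOVA leaves out three of the four randomisation factors: a small, avoidable loss of precision if those factors are prognostic

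*Combined protocol and SAP*

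**What the plan says.** Section 7 sets up randomisation within strata: "Eligible subjects will be stratified based on the Pre-treatment Schiff Index and Yeaple probe sensitivity scores, age, and gender". The table there gives two levels for each factor: Schiff at or below 2.5 versus above, "Pre-treatment Yeaple Probe" equal to 10 versus above 10, age under 40 versus 40 and over, and gender. That makes 2 × 2 × 2 × 2 = 16 strata, with a block size of 4. One exception to individual randomisation is stated: "Subjects from the same household will be assigned to the same treatment group".

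Section 14 first reduces the data to one value per subject and visit: "Sensitivity scores will be averaged amongst test teeth within each subject for each assessment before and after treatment". It then gives the only between-group model: "mean comparisons between treatment groups will be analyzed using analysis of covariance with the" "baseline score as a covariate with either non-parametric or parametric methods". The same section allows further methods in general terms but names none. Section 13 identifies the main comparison: "The Schiff Index Sensitivity Scale at Week 4 will be of primary interest".

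**The concern.** The sponsor thought four factors worth balancing, yet each model uses only one of them. Stratified allocation makes the arms alike on all four, so the true sampling variance of the treatment difference falls when the factors are prognostic. A model that ignores three of them does not register this: it estimates the residual variance as if their contribution were noise. The reported standard error is then too large, the test rejects under the null less often than 5%, and the confidence interval is wider than it needs to be.

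This applies to every between-group comparison, including the Week 4 Schiff comparison. What is at stake is some precision, not validity. There is also a pre-specification point: without a named covariate set, an analysis adjusted for the randomisation factors could only be presented as an unplanned extra.

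**Working it through.** **Inputs from Section 10.** Two-sided α = 0.05; 28 completers per group; Schiff difference 0.80 with SD 0.88; Yeaple difference 10.97 with SD 12.44. Four groups give 4 × 28 = 112 completers.

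**Step 1: the plan's own power.** The standard error of a difference is SD × √(2/28).

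- Schiff: 0.88 × 0.2673 = 0.2352; noncentrality 0.80 / 0.2352 = 3.40.
- Yeaple: 12.44 × 0.2673 = 3.325; noncentrality 10.97 / 3.325 = 3.30.

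Residual df are 112 − 4 arms − 1 covariate = 107 as planned, and 104 with three more covariates. Noncentral t power:

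| | two-group t, 54 df | planned ANCOVA, 107 df | three covariates added, 104 df |
|---|---|---|---|
| Schiff | 91.63% | 92.09% | 92.07% |
| Yeaple | 89.98% | 90.49% | 90.47% |

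The stated 90% is reproduced, and losing three df costs almost nothing in itself.

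**Step 2: what adjustment changes.** Let R² be the share of the variance left after own-baseline adjustment that the three omitted factors explain. The documents give no value, so 0 to 15% is an assumed illustration, not a bound. Shrinking the SD by √(1 − R²) and comparing 107 with 104 df would suggest Schiff gains of 1.2, 2.35 and 3.4 points at 5, 10 and 15%. That overstates the gain, because stratification already lowers the true variance of the unadjusted difference. Simulation is needed.

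**Step 3: simulation.** Each run has 120 subjects, the 16 strata, permuted blocks of 4 and 8 random dropouts. Further assumptions: averaged baseline Schiff 2/2.5/3 with probabilities 0.40/0.25/0.35; Yeaple 10/15/20 with 0.5/0.3/0.2; age normal (mean 42, SD 12) truncated at 18; gender 50:50; normal errors; equal factor effects; 0.88 and 12.44 read as SDs after own-baseline adjustment. A single four-arm model is fitted, with 100,000 runs per setting and Monte Carlo SE below 0.1 point.

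| R² | Schiff power, planned vs adjusted (change) | Yeaple power, planned vs adjusted (change) | Type I error as planned, Schiff / Yeaple |
|---|---|---|---|
| 0% | 91.9 vs 91.6 (−0.26) | 90.4 vs 90.1 (−0.31) | 5.1 / 5.0% |
| 5% | 92.1 vs 92.8 (+0.71) | 90.4 vs 91.3 (+0.82) | 4.5 / 4.5% |
| 10% | 92.5 vs 94.0 (+1.53) | 91.0 vs 92.7 (+1.70) | 4.2 / 4.3% |
| 15% | 93.1 vs 95.3 (+2.27) | 91.3 vs 94.0 (+2.68) | 3.8 / 3.9% |

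Adjusted type I error is 4.9–5.1%. At R² = 20% the gains are +2.9 and +3.6 points, so 15% is not a ceiling.

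The mechanism shows for Schiff at 15%. The planned model reports an SE of 0.236 while the true SD is 0.224; the adjusted SE is 0.218. The effective critical value is 1.982 × 0.236 / 0.224 = 2.09, which corresponds to a two-sided error of about 3.9%, in line with the table. The 95% half-width falls from 1.982 × 0.236 = 0.47 to 1.983 × 0.218 = 0.43. At R² = 5 and 10% the adjusted half-widths are 0.46 and 0.45.

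**Step 4: sensitivity.** The four-arm model was rerun with:

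- 30% of subjects in same-household pairs sharing an arm;
- all R² on one factor;
- true effects as steps at the randomisation cut-offs, with continuous covariates fitted;
- scores rounded to half-steps or 5 g steps, with the Section 12 ceiling ("If no sensitivity is found up to 50 g, 50 will be recorded as the threshold");
- the rank-based analysis.

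Over all these cases the change is −0.4 to −0.1 points at R² = 0, +0.6 to +0.9 at 5%, +1.0 to +2.0 at 10% and +1.6 to +3.1 at 15%. The step-effect case gives the low end: Schiff +1.0 and +1.6 at 10 and 15%.

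**Step 5: how plausible are these R² values?** With equal effects and a 50:50 split, the gender shift needed beyond own baseline is 2 × SD × √(R²/3). For Schiff that is 0.23, 0.32 and 0.39 units at 5, 10 and 15%; for Yeaple 3.2, 4.5 and 5.6 g. These are 28–51% of the design differences. Inclusion criterion 11 also narrows both baselines. The low end deserves most weight.

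**The case against.** The strongest reply is that both models are valid and no passage requires the covariates to mirror the strata. The benefit depends wholly on an R² the documents do not supply, and the low end is the more plausible. Straight-line interpolation of the Schiff results puts break-even at 5 × 0.26 / (0.26 + 0.71) ≈ 1.3%. At R² = 2%, a simulation of 12,000 runs gave +0.2 points in the four-arm model and −0.2 with separate two-arm models, which is effectively zero.

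Section 14 also does not say whether comparisons come from one four-arm model. With two-arm models and evenly split factors, a separate simulation gave Schiff changes of −0.37, +0.34, +1.22 and +2.06 at 0, 5, 10 and 15%; at 5% that is below the range in Step 4. In two-arm models the cost with uninformative factors is about 0.4 to 0.6 points. Finally, entering age as continuous does not reproduce the cut at 40.

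These points stand and limit the size of the finding. They do not remove it. The omission is unexplained, the possible loss is small, and the possible gain is larger than the loss unless the factors are close to uninformative. Continuous age still gains power, with adjusted type I error of 4.9–5.0%, in the step-effect case.

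**Conclusion.** The concern holds and is minor. Three of the four randomisation factors are absent from each between-group model without explanation. The consequence is conditional on those factors being prognostic: for R² of 5 to 15%, the planned test gives up roughly 0.7 to 2.3 points of power for Schiff and 0.8 to 2.7 for Yeaple, and its true type I error falls to about 4.5 to 3.8%. Nothing is biased, and the power claim in Section 10 stands with or without the change. The figures rest on the assumed R², the assumed baseline distributions, a four-arm model and the reading of 0.88 and 12.44 as baseline-adjusted SDs, which Section 10 does not specify. The direction is firmer than the exact size.

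**What to change.** Amend Section 14 to pre-specify, for each post-treatment assessment and explicitly for the Week 4 Schiff comparison:

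> Treatment groups will be compared by analysis of covariance with treatment, baseline Schiff score, baseline Yeaple score, age (continuous) and gender as main effects. If a rank-based analysis is used, the same covariates will be included.

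Use main effects only; 16 stratum cells are too many for 112 completers. In the rank-based version, rank the outcome, both baselines and age, and keep gender as an indicator. State that the comparisons come from one four-arm model. If the three factors are omitted on purpose, a sentence giving the reason is enough.

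The cost is one sentence and no new data, since all four variables are collected at Visit 1. The downside is three degrees of freedom (107 to 104) and, if none of the factors is prognostic, about 0.3 points of power (0.1 to 0.4 over the four-arm cases run).
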